² Screening laboratory tests include: ALT, AST, creatinine (and calculate an estimated glomerular filtration rate (eGFR) the formula used is determined by the sites, but should be consistent throughout the study), and urine or serum pregnancy test for females of child-bearing potential. Laboratory tests performed as part of routine clinical care in the 48 hours prior to enrollment will be accepted for determination of eligibility.

³ Baseline assessments should be performed prior to first infusion. Laboratory tests performed as part of routine clinical care in the 24 hours prior to first dose will be accepted for the baseline safety laboratory tests. Baseline may be the same as the screening laboratory tests if obtained in the 24 hours prior to first dose.

⁴ Safety laboratory tests include WBC with differential, hemoglobin, platelets, creatinine, total bilirubin, ALT, AST, and INR.

⁵ Any laboratory tests performed as part of routine clinical care within the specified visit window can be used for safety laboratory testing. ⁶ In-person visits are preferred but recognizing quarantine and other factors may limit the subject's ability to return to the site for the visit. In this case, the visit may be performed by phone.

- If still hospitalized at Day 15 and 29 or returns for an in-person visit: assess adverse events, collect clinical data, vital signs, safety laboratory tests, and research laboratory samples (OP swab and blood) as able.
- If phone call only on Days 15 and 29 and all Day 22 and Day 60 visits: assess adverse events, clinical status (ordinal scale), readmission to a hospital, and mortality only.

⁷ Oropharyngeal swabs are preferred, but if these are not obtainable, saliva or nasopharyngeal or nasal swabs may be substituted. ⁸ Pre-dose serum sample collections for PK and immunogenicity.

⁹ To include markers of inflammation and coagulation: CRP, ferritin, fibrinogen, d-dimer.

¹⁰ Day 8, 22 and 60 visits performed by phone call or home visit if discharged from the site hospital: assess adverse events, clinical status (ordinal scale), readmission to a hospital, and mortality only.

¹¹ Only collected at selected sites capable of processing.

¹² Steroids and other concomitant therapies intended as specific treatment of COVID-19, as well as all biologics, will be assessed from 7 days prior to enrollment to Day 29. All other concomitant medications will be assessed from 7 days prior to enrollment to Day 15 or upon discharge, whichever comes first.

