8.1.2.1 Measures of Clinical Support, Limitations, and Infection Control

The subject's clinical status will be captured on each study day while hospitalized up until and including Day 29. Once subjects are discharged from the hospital, they will have a study visit on Days 8, 15, 22, 29, and 60 visits (only the ordinal score will be obtained on Day 60) as an outpatient. The Day 8, Day 22 and Day 60 visits do not have laboratory tests or collection of samples and may be conducted by phone. Day 15 and 29 visits are preferred to be in person in order to collect safety laboratory testing, stored samples, and virologic assessments but may be performed. Clinical status is largely measured by the ordinal scale. The ordinal scale can also be evaluated over the phone if the discharged subject is unable to return for in-person visits on Day 15 and 29.

The following measures are recorded for the ordinal scale. See MOP for more detailed description of ventilatory devices in each category:

- Hospitalization.
- Oxygen requirement.
- Non-invasive mechanical ventilation (via mask) requirement.
- High-flow oxygen requirement.
- Invasive mechanical ventilation (via endotracheal tube or tracheostomy tube) requirement.
- ECMO requirement.
- Ongoing medical care preventing hospital discharge (COVID-19 related or other medical conditions).
- Limitations of physical activity (self-assessed and reported as new or increased limitations as compared to status prior to the onset of COVID-19).
- Isolated for infection control purposes.

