3.2. Endpoints

Primary Endpoint

The default primary endpoint is clinical status (8-point ordinal scale) on Study Day 8:

1. Not hospitalized, no new or increased limitations on activities;
2. Not hospitalized, but new or increased limitation on activities and/or requiring new or increased home oxygen, CPAP, or BiPAP;
3. Hospitalized, not requiring new or increased supplemental oxygen - no longer requires ongoing medical care;
4. Hospitalized, not requiring new or increased supplemental oxygen - requiring ongoing medical care (COVID-19 related or otherwise);
5. Hospitalized, requiring new or increased supplemental oxygen;
6. Hospitalized, requiring new or increased non-invasive ventilation or high-flow oxygen devices;
7. Hospitalized, on invasive mechanical ventilation or extracorporeal membrane oxygenation (ECMO);
8. Death.

Key Secondary Endpoints

One of the key secondary endpoints is time to sustained recovery (up to and including Study Day 60) and is defined as the first day on which the subject satisfies 1 of the following 3 categories from the clinical status ordinal scale (and does not return to a score of ≥ 4 up to and including Study Day 60):

1. Not hospitalized, no new or increased limitations on activities;
2. Not hospitalized, but new or increased limitation on activities and/or requiring new or increased home oxygen, CPAP, or BiPAP;
3. Hospitalized, not requiring new or increased supplemental oxygen - no longer requires ongoing medical care.

The other key secondary endpoint is whether the subject did not satisfy one of the following two categories from the ordinal scale up to and including Study Day 29. This analysis will only be completed for those subjects with baseline ordinal score of 5 or 6:

7. Hospitalized, on invasive mechanical ventilation or ECMO;
8. Death.

If the key secondary endpoints are different than what is covered in this master SAP, it will be highlighted for each individual investigational intervention in the corresponding stage-specific appendix.

Other Secondary Endpoints

The other secondary endpoints are:

Efficacy

- Time (days) from Study Day 1 to the first day for which a subject is assessed to be at least 1 category lower (improvement) than the subject's baseline ordinal score up to and including Study Day 60;
- Time (days) from Study Day 1 to the first day for which a subject is assessed to be at least 2 categories lower (improvement) than the subject's baseline ordinal score up to and including Study Day 60;

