4.5. Efficacy and Safety Variables

For each study day while the subject is hospitalized and follow-up visits, the clinical status will be recorded on an 8- point ordinal scale. The clinical status scale is defined as follows:

1. Not hospitalized, no new or increased limitations on activities;
2. Not hospitalized, but new or increased limitation on activities and/or requiring new or increased home oxygen, CPAP or BiPAP;
3. Hospitalized, not requiring new or increased supplemental oxygen* - no longer requires ongoing medical care;
4. Hospitalized, not requiring new or increased supplemental oxygen* - requiring ongoing medical care (COVID-19 related or otherwise);
5. Hospitalized, requiring new or increased supplemental oxygen*;
6. Hospitalized, requiring new or increased non-invasive ventilation or high flow oxygen devices;
7. Hospitalized, on invasive mechanical ventilation or ECMO;
8. Death.

The National Early Warning Score (NEWS) has demonstrated an ability to discriminate subjects at risk of poor outcomes [1]. This score is based on 7 clinical parameters (see Table 3). The NEWS is collected at baseline as a measure of ordinal score. It can be performed concurrently with the Ordinal Scale.

The 7 parameters can be obtained from the hospital chart or electronic medical record (EMR) using the last measurement prior to the time of assessment and a numeric score given for each parameter (e.g., a RR of 9 is one point, oxygen saturation of 92 is two points). The NEWS is recorded for the day on which it is obtained. ECMO and mechanical ventilated subjects should be assigned a score of 3 for respiratory rate (RR<8) regardless of the ventilator setting. Subjects on ECMO should get a score of 3 for heart rate since they are on cardiopulmonary bypass.

Table 3: National Early Warning Score (NEWS)

PHYSIOLOGICAL PARAMETERS	3	2	1	0	1	2	3
Respiration Rate	≤8		9 - 11	12 - 20		21 - 24	≥25
Oxygen Saturations	≤91	92 - 93	94 - 95	≥96			
Any Supplemental Oxygen		Yes		No			
Temperature	≤35.0		35.1 - 36.0	36.1 - 38.0	38.1 - 39.0	≥39.1	
Systolic BP	≤90	91 - 100	101 - 110	111 - 219			≥220
Heart Rate	≤40		41 - 50	51 - 90	91 - 110	111 - 130	≥131
Level of Consciousness				A			V, P, or U

Level of consciousness = alert (A), and non-alert and arousable only to voice (V) or pain (P), and unresponsive (U).

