Analysis of time to event endpoints (i.e., sustained recovery, time to improvement, time to mechanical ventilation or death) will be based on observed ordinal score without imputation along with discharge and death information. Refer to Table 7 for additional details regarding censoring and handling of missing data for all endpoints. As handling of missing data might differ for different stages of this study, stage-specific SAPs will provide additional details if handling of missing data for an endpoint for that stage differ from what is in the master SAP.

Table 7: Imputation Method for Each Endpoint and Analysis Type

Endpoint	Analysis	Imputation Method
Primary Endpoint		
1. Ordinal Score at Day 8	Primary	
 • If a subject is discharged from the hospital to another location other than LTAC, hospice care or other hospital, has intermittent missing ordinal score and reported an ordinal score of 1 or 2 after the missing score then: 
 ○ Impute the intermittent missing ordinal score as 1 if the scores reported before and after the missing value are both 1 and no change in oxygen use or hospitalization status after discharge to a location other than hospice, long term acute care or other hospital. ○ Impute the intermittent missing ordinal score as 2 after discharge to a location other than hospice, long term acute care or other hospital if the subject doesn't fall into the category above and subject is not hospitalized at the time point. • LOCF will be used for remaining intermittent missingness of ordinal scores for the next planned assessment. • All missing scores after death will be assigned an ordinal score of 8.

Endpoint	Analysis	Imputation Method
		
 Subjects discharged from the hospital to a location other than LTAC, hospice care or other hospital at their last assessment will be assigned a score of 2 for all timepoints after last assessment. Multiple imputation will be used to impute missing ordinal scores after last assessment for subjects still hospitalized or discharged to hospice, other hospital, or long-term care facility at their last assessment. See Section 6.5.2 for more details.

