	Primary with Sensitivity Imputation 1	
 Use similar imputation methods for intermittent missingness and missing data after death. Multiple Imputation will be used for all subjects missing data after last assessment regardless of their discharge status at the last assessment.
	Primary with Sensitivity Imputation 2	
Use complete data defined as follow:
 
 If a subject is discharged from the hospital to another location other than LTAC, hospice care or other hospital, has intermittent missing ordinal score and reported an ordinal score of 1 or 2 after the missing score then: 
 Impute the intermittent missing ordinal score as 1 if the scores reported before and after the missing value are both 1 and no change in oxygen use or hospitalization status after discharge to a location other than hospice, long term acute care or other hospital. Impute the intermittent missing ordinal score as 2 after discharge to a location other than hospice, long term acute care or other hospital if the subject doesn't fall into the category above and subject is not hospitalized at the time point. LOCF will be used for remaining intermittent missingness of ordinal scores for the next planned assessment. All missing scores after death will be assigned an ordinal score of 8 Subjects discharged from the hospital to a location other than LTAC, hospice care or other hospital at their last assessment will be assigned a score of 2 for all timepoints after last assessment. Impute all remaining missing data after last assessment using last observation carried forward.
	Sensitivity	
 Same imputation as the primary analysis
	Supplemental	
 Same imputation as the primary analysis
	Subgroup	
 Repeat analysis for each subgroup using same imputation as primary analysis for this endpoint.
Key Secondary Endpoints		
1. Time to Sustained Recovery	Primary	
 Use the complete data for ordinal score to derive sustained recovery. Subjects whose last assessment in the study is prior to Day 57 (beginning of Day 60 window) will be considered not recovered and censored at the date of their last assessment. Death prior to recovery will be considered not recovered and censored at expected study Day 60.

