8.2. Secondary Efficacy Analyses

8.2.1. Key Secondary Efficacy Analyses

Recovery will be defined as having a value of 1, 2, or 3 on the clinical status 8-point ordinal scale. The time to sustained recovery will be defined as the elapsed time (in days) from Study Day 1 to the day prior to the earliest recorded day at which a subject reaches recovery or hospital discharge and doesn't worsen (ordinal score > 3) up to and including Study Day 60. For example, a hospitalized subject with an ordinal score of 3 on Study Day 7 and doesn't worsen up to and including Day 60 will have a time to sustained recovery of 6 days, since ordinal score is reflective of the prior 24-hours.

For the primary analysis of sustained recovery endpoint, any subjects whose last assessment in the study is prior to an observed recovery will be censored at the day of their last observed assessment. For the sensitivity analysis of this endpoint, subjects whose last assessment in the study is prior to an observed recovery before Day 57 (beginning of Day 60 window) and who were discharged to a location other than LTAC, hospice care, or other hospital will be considered recovered and censored at Day 60. For both primary and sensitivity analysis of this endpoint, subjects who complete follow-up but do not experience sustained recovery will be censored at the day of their Study Day 60. All deaths that occur on or before Study Visit Day 60 will be considered not recovered and censored at Day 60. Note that we do not expect many subjects to worsen after discharge.

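### No fixed rule makes a readmission end sustained recovery, and no ordinal score is scheduled on Days 30 to 59

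*SAP*

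**What the plan says.** **Definition.** SAP 3.2 takes the first day in category 1, 2 or 3, provided the subject recovers "and does not return to a score of ≥ 4 up to and including Study Day 60". Protocol Table 3 sets the same condition for the rest of the study. Category 4 is a hospitalized subject without new or increased oxygen but "requiring ongoing medical care (COVID-19 related or otherwise". Category 3 is also a hospitalized state, but without that need, and it counts as recovered.

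**Derivation.** The text of SAP 6.5.1 says the analysis "will be based on observed ordinal score without imputation along with discharge and death information". Table 7, in the same section, says "Use the complete data for ordinal score to derive sustained recovery". SAP 8.2.1 counts to the day before the earliest day on which the subject "reaches recovery or hospital discharge and doesn't worsen (ordinal score > 3) up to and including Study Day 60".

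**Schedule.** Under Protocol 8.1.2.1, "clinical status will be captured on each study day while hospitalized up until and including Day 29". Discharged subjects are contacted on Days 8, 15, 22, 29 and 60.

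**Readmission data.** Footnotes 6 and 10 to the Protocol 1.2 schedule say that phone or home contacts, including Day 60, cover adverse events and "clinical status (ordinal scale), readmission to a hospital, and mortality only". Protocol 8.1.2.1 says that "only the ordinal score will be obtained on Day 60", and footnote 13 says the same of the Day 60 clinical data entry.

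**Committee.** SAP 8.2.1 lets the ERC weigh readmittance information for subjects discharged to hospice or another hospital, or when the handling of recovery is unclear.

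**The concern.** The definition describes an unbroken period, but the derivation tests isolated days. SAP 8.2.1 treats a score as reflecting the prior 24 hours, and after Day 29 the next score is at Day 60. A relapse into hospital that begins and ends inside that gap leaves no trace in the ordinal series. The resulting error runs one way: a subject who lost recovery is counted as having kept it, from the earliest date.

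The SAP deals with comparable gaps for other endpoints in 8.2.2. Oxygen and ventilation days have a rule for planned gaps and a post-discharge form for time away from the study hospital, and hospital days count readmissions. The first key secondary endpoint has no such rule. At stake are the count of sustained recoveries and the recovery times of the affected subjects.

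**Working it through.** The plan gives no event count, power figure or readmission rate for this endpoint, so there is no planned figure to reproduce. The check is a trace through the rules followed by a count of unscored days.

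**1. One subject under the definition and under the rule.** Suppose a subject is discharged on Day 7, is readmitted on Day 35 needing ongoing medical care, is discharged again on Day 44, and scores 1 or 2 at the Day 8, 15, 22, 29 and 60 contacts.
- Under the definition in SAP 3.2, the subject was in category 4 or higher from Day 35, so recovery from Day 7 was not sustained.
- Under SAP 6.5.1, Table 7 and 8.2.1, no recorded score exceeds 3, so the subject is an event at 7 − 1 = 6 days.
- If the readmission counted, recovery would date from the second discharge: 44 − 1 = 43 days.

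Reading the discharge information in SAP 6.5.1 generously does not change this. In 8.2.1, discharge is a way to reach recovery; nothing there makes an admission a way to lose it.

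**2. Unscored days.** Contact days are from Protocol 8.1.2.1 and windows from SAP Table 1.
- Between the Day 8, 15, 22 and 29 contacts: 7 − 1 = 6 days each.
- Between Day 29 and Day 60: 60 − 29 − 1 = 30 days (Days 30 to 59).
- With windows of 26–32 and 57–63, the last gap is between 57 − 32 − 1 = 24 and 63 − 26 − 1 = 36 days.

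The short gaps matter less. A stay on or before Day 29 may be scored daily if in-hospital scoring resumes on readmission. Whether it does cannot be settled here, because Protocol 7.3 refers to a Master protocol section that is not among these documents.

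**3. Share of late readmissions with no scored day.** Assume (not from the documents) that a stay starts with equal probability on each of Days 30 to 59, lasts L days, and that the Day 60 score is taken on Day 60. The stay includes Day 60 when it starts on Day 61 − L or later, which is L − 1 of the 30 possible starts. The share missed is (31 − L)/30.

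| L (days) | Missed | Share |
|---|---|---|
| 3 | 28/30 | 93% |
| 5 | 26/30 | 87% |
| 7 | 24/30 | 80% |
| 10 | 21/30 | 70% |
| 14 | 17/30 | 57% |

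**4. Illustrative counts.** With an assumed readmission rate r on Days 30 to 59, uncounted relapses per 100 subjects are 100 × r × (31 − L)/30.
- r = 2%, L = 14: 100 × 0.02 × 17/30 = 1.1
- r = 5%, L = 7: 100 × 0.05 × 24/30 = 4.0
- r = 10%, L = 3: 100 × 0.10 × 28/30 = 9.3

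**The case against.** A reader might infer that readmissions play no part in this endpoint. The documents do not support that. The ERC may consider readmittance information, may ask for more, and may decide whether and when recovery was sustained; SAP 6.5.1 allows it to adjudicate key secondary endpoints before the Table 7 rules apply. What remains is that the review is discretionary and that a readmission does not prompt it.

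A reader might also treat every inpatient readmission as a score of 4 or more. That fails too, because category 3 is a hospitalized recovery state; the need for ongoing medical care is what matters.

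It is tempting to add that the treatment comparison is biased, or that a late difference between arms is hidden for an antibody with a half-life of about 28 days. Nothing in the documents shows that missed readmissions would differ by arm, and no effect on the median or hazard ratio has been calculated. SAEs and a safety composite through Day 60 are reported by arm (SAP 9.3 and 9.4), so late events would still show there.

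Three further points stand. The SAP expects few subjects to worsen after discharge. The promising or significant declaration rests on the Day 8 score. The Day 60 conflict is narrower than it looks: in the SAP's copy of the schedule (Table 10), footnote 13 is attached only to clinical data collection, and adverse event evaluation has its own Day 60 mark. The open question is whether readmission and mortality are asked about at Day 60.

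Finally, one can say that the protocol defines the endpoint by scores and the SAP follows it. But the condition runs through Day 60, and the scale classes a readmission needing care as 4 or more whether or not anyone records the score.

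**Conclusion.** The point holds in this form: apart from an optional ERC review that readmission does not trigger, no rule makes a recorded readmission count as loss of sustained recovery, and Days 30 to 59 carry no scheduled score. A subject readmitted for ongoing care in that gap and home at Day 60 is classified against the endpoint's own definition.

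That conclusion rests on the text alone. Its size is unknown. The 57% to 93% range depends on uniform start days and stays of 3 to 14 days. The range of about 1 to 9 uncounted relapses per 100 subjects also depends on an assumed readmission rate of 2% to 10%. The rule should be corrected, but the gap does not touch the primary analysis, and a distorted treatment effect on this endpoint has not been shown.

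**What to change.** In SAP 6.5.1, 8.2.1 and the Table 7 entry for time to sustained recovery, state three things:
- A recorded readmission needing ongoing medical care, from any cause (as category 4 is defined), after first recovery and through Day 60 counts as a return to a score of 4 or more.
- Sustained recovery is then dated from the first later score of 1 to 3, or discharge, that is not followed by worsening.
- Unclear cases must go to the blinded ERC.

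Reconcile Protocol 8.1.2.1 and footnote 13 with footnotes 6 and 10, so that readmission, with dates, is collected at Day 60. In the same edit, settle whether sustained recovery uses observed scores without imputation (SAP 6.5.1 text) or the complete data, which are imputed (Table 7).

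The cost is one derivation rule and some wording. Footnotes 6 and 10 already ask about readmission but do not name dates. SAP 4.5 already uses admission and discharge dates for hospital days, and Listing 13 carries hospitalization date and reason; it should be confirmed that these reach Day 60, since the hospital-days endpoint stops at Day 29. The downside is slightly fewer or later recoveries.

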Remaining missing ordinal scores for subjects that terminated early from the study and were still hospitalized at the time of their last assessment or with discharge to a location of hospice, LTAC or other hospital at the time of last contact will be imputed using multiple imputation. A sensitivity analysis of this analysis will be

performed using multiple imputation for all subjects missing ordinal after their last assessment regardless of their discharge status at the last assessment. Details of multiple Imputation are provided in Section 6.5.2.

Some analyses of ordinal score such as those reported in Table 17, Table 18, Table 20, Table 21, Table 24, Table 25, Table 26, Table 27, Table 34, Table 35, Figure 4, Figure 5, Figure 6, Figure 7, and Figure 18 will be based on complete ordinal score data created using the following steps:

- If a subject is discharged from the hospital to a location other than LTAC, Hospice care or other hospital, has intermittent missing ordinal score and reported an ordinal score of 1 or 2 after the missing score then:
 - Impute the intermittent missing ordinal score as 1 if the scores reported before and after the missing value are both 1 and no change in oxygen use or hospitalization status after discharge to a location other than hospice, long term acute care or other hospital.
 - Impute the intermittent missing ordinal score as 2 after discharge to a location other than hospice, long term acute care or other hospital if the subject doesn't fall into the category above and subject is not hospitalized at the time point.
- LOCF will be used for remaining intermittent missingness of ordinal scores for the next planned assessment.
- All missing scores after death will be assigned an ordinal score of 8.
- Subjects discharged from the hospital to a location other than LTAC, hospice care or other hospital at their last assessment will be assigned a score of 2 for all timepoints after last assessment.
- Impute all remaining missing data after last assessment using last observation carried forward.

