	Primary with Sensitivity Imputation 1	
 Use the complete data for ordinal score to derive sustained recovery. Subjects whose last assessment in the study is prior to Day 57 (beginning of Day 60 window) after discharge from the hospital to a location other than LTAC, hospice care or other hospital will be treated as recovered by Day 60. Their time to recovery will be the day of their first observed/imputed recovery score (i.e., 1, 2, 3) or the day of discharge, whichever comes first. Subjects whose last assessment in the study is prior to Day 57 (beginning of Day 60 window) without being discharged from the hospital to a location other than LTAC, Hospice care or other hospital at their last assessment will be considered not recovered and censored at the date of their last assessment.

Endpoint	Analysis	Imputation Method
		
 Death prior to recovery will be considered not recovered and censored at expected study Day 60.
	Supplementary	
 Same imputation method as primary analysis for time to sustained recovery.
	Subgroup	
 Repeat analysis for each subgroup using same imputation as primary analysis for this endpoint.
2. Survival without respiratory failure up to and including Study Day 29	Primary	
 Subjects who complete follow-up without mechanical ventilation or death or who have the event after Day 29 will be considered non-events and censored at Day 29. Subjects whose last assessment in the study is before Day 26 (beginning of Day 29 window) and before experiencing death or progression to mechanical ventilation will be considered non-events and censored at the last assessment. Subjects whose last assessment in the study is before Day 29 but within window for Day 29 (i.e., Day 26, 27, 28) and before experiencing death or progression to mechanical ventilation will be considered non-events regardless of their discharge status and censored at Day 29.

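### The sensitivity analysis of sustained recovery can date recovery before a recorded relapse, and the SAP gives the same subjects conflicting event dates and status

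*SAP*

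**What the plan says.** SAP Section 3.2 defines time to sustained recovery as the first day in category 1, 2 or 3, provided the subject "does not return to a score of ≥ 4 up to and including Study Day 60". Section 8.2.1 repeats the no-worsening condition.

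Table 7 in Section 6.5.1 sets the handling of losses. Its sensitivity row for this endpoint has these parts:

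- **Status.** Subjects last assessed before Day 57 after a good discharge "will be treated as recovered by Day 60".
- **Date.** "Their time to recovery will be the day of their first observed/imputed recovery score" or the discharge day, whichever is earlier.
- **Limit.** Subjects last assessed before Day 57 "without being discharged from the hospital to a location other than LTAC, Hospice care or other hospital at their last assessment" are not recovered and are censored at that assessment.
- **Death.** "Death prior to recovery will be considered not recovered and censored at expected study Day 60".

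Section 8.2.1 words the death rule differently: "All deaths that occur on or before Study Visit Day 60 will be considered not recovered and censored at Day 60".

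Three other statements cover the same sensitivity group. One paragraph of Section 8.2.1 calls these subjects recovered and also censors them at Day 60. The next dates recovery at discharge and allows, without requiring, review by the Endpoint Review Committee. Table 28 footnote b calls them recovered at Day 60.

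**The concern.** The dating sentence takes the first recovery score, and the endpoint is recovery that lasts. For most subjects these coincide. They part when a score of 1–3 is followed by a recorded return to 4 or higher, then a good discharge, then loss before Day 57. The literal rule places that subject's event before a relapse that is in the database.

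This row is the only alternative missing-data handling planned for the endpoint, since Table 7 gives the supplementary and subgroup analyses the primary handling. Its purpose is to show what happens when good-discharge losses count as recovered instead of censored. If it also redefines recovery for some of them, a difference from the primary result no longer reflects that one choice. Four statements that disagree on date or status also leave the programmer to decide which analysis is run.

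**Working it through.** No sample-size or power figure is involved, so the check applies the stated rules to constructed subject histories.

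**The plan's own example first.** Section 8.2.1 gives a score of 3 on Study Day 7 with no later worsening a time of 6 days. The convention is study day minus one: 7 − 1 = 6, which reproduces.

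**Rules compared.** (i) The Table 7 sensitivity row read literally: good discharge at a last assessment before Day 57 is recovered, dated at the earlier of the first score of 1–3 and discharge; otherwise censored at the last assessment. (ii) The Section 3.2 no-return condition together with the Section 8.2.1 death rule.

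| History (constructed) | Table 7 row, literal | Definition plus Section 8.2.1 death rule |
|---|---|---|
| A: score 3 on Day 5, score 5 on Day 6, score 6 on Day 7, home Day 20, last seen Day 29 | Recovered Day 5 | Recovered Day 20 |
| B: home Day 6, readmitted Day 12, home again Day 20, last seen Day 29 | Recovered Day 6 | Recovered Day 20 |
| C: home Day 6, readmitted Day 12, last seen in hospital Day 15 | Censored Day 15 | Censored Day 15 |
| D: home Day 6, last visit Day 29, died Day 40 | Recovered Day 6, if the good-discharge bullet is read alone | Not recovered, censored Day 60 |
| E: home Day 6, no relapse, last seen Day 29 | Recovered Day 6 | Recovered Day 6 |

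**Size per subject.** In A the recorded time is 5 − 1 = 4 days instead of 20 − 1 = 19, so 15 days too early. In B it is 6 − 1 = 5 instead of 19, so 14 days too early. C and E are unaffected.

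**Consistency of the four statements.** For A, the paragraph of Section 8.2.1 that dates recovery at discharge gives Day 20, against Day 5 in Table 7. For B, that paragraph does not say whether the Day 6 or the Day 20 discharge counts. Even for E, where no relapse occurs, Table 7 and that paragraph give an event on Day 6, the preceding paragraph of Section 8.2.1 gives recovery with censoring at Day 60, and Table 28 footnote b read as a date gives recovery at Day 60. These cannot all be programmed.

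**The case against.** A reader might infer that post-discharge deaths will be counted as early recoveries. The documents do not support that. The Section 8.2.1 rule covers every death through Day 60, with no exception for deaths after discharge, and directly follows a sentence on both the primary and the sensitivity analysis. The first bullet of the Table 7 row derives sustained recovery from the complete data, where "All missing scores after death will be assigned an ordinal score of 8", so a death after discharge is itself a return to 4 or higher. The same narrow death wording also stands in Table 7's primary row, which suggests shorthand. What remains is that the row's wording is narrower than Section 8.2.1 and should be aligned.

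A reader might also infer that any relapse in a subject once discharged home is lost. It is not: a subject back in hospital when last assessed is censored by the next bullet, as in history C.

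It can fairly be said that Section 8.2.1 dates this group at discharge, which gives the right day in history A, that the committee can review odd cases, and that the complete-data bullet carries the endpoint definition into the row. These help only in part. Section 8.2.1 sends the reader to Table 7 for imputation, and Table 7 gives this group its own explicit date after the complete-data bullet. Committee review is optional. The authors did write conditions where they wanted them: the matching sensitivity row for survival without respiratory failure limits losses to those before death or ventilation, and the recovery row has no counterpart.

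Finally, Section 8.2.1 expects few subjects to worsen after discharge, and Section 6.5.1 expects little missing data. Both points stand and make the affected group likely small. The first does not cover a relapse in hospital before discharge, as in history A.

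**Conclusion.** The point holds in a narrow form. Read literally, the Table 7 sensitivity row dates recovery before a recorded relapse for subjects who go through four steps: a score of 1–3, a recorded return to 4 or higher, a later good discharge, and loss before Day 57. In the constructed histories the event is 14 to 15 days early. Those histories illustrate the rule and do not estimate frequency. The documents give no relapse or loss rates, so neither the number of affected subjects nor the shift in the hazard ratio can be calculated.

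The death wording is a conflict between Table 7 and Section 8.2.1, not evidence that deaths will be coded as recoveries. The differing dates and statuses in Table 7, Section 8.2.1 and Table 28 footnote b are a further conflict that touches every good-discharge loss, relapsed or not.

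The primary analysis is not affected by the dating rule, because Table 7's primary row censors subjects last assessed before Day 57. The matter is confined to one sensitivity analysis of a key secondary endpoint, but it should be settled before that analysis is programmed.

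**What to change.** Three wording changes in the SAP:

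1. In Table 7, Time to Sustained Recovery, Sensitivity Imputation 1, date recovery at the first score of 1–3 or good discharge that is not followed by any recorded score of 4 or higher. This also settles which discharge counts after a readmission.
2. Replace that row's death bullet with the Section 8.2.1 rule, so that every death on or before Day 60 is not recovered and is censored at Day 60. Use the same wording in the primary row.
3. Make both paragraphs of Section 8.2.1 that describe this sensitivity group, and Table 28 footnote b, state the same status (an event) and the same date as the revised Table 7. Remove the wording that makes the subject both recovered and censored.

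The cost is SAP text and one derivation rule. No new data are needed, and the primary analysis does not change.
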